# 12.5. Procedures to be Followed in the Event of Abnormal Laboratory Test Values

In the event of unexplained abnormal laboratory test values, the tests should be repeated immediately and followed up until they have returned to the normal range and/or an adequate explanation of the abnormality is found. Abnormal laboratory values or test results constitute AEs only if they induce clinical signs or symptoms, are considered clinically significant, or require therapy. For abnormal laboratory test values related to AEs of special interest refer to Section 12.4.

# 12.6. Clinical Laboratory Parameters and Abnormal Laboratory Test Results

Clinically significant changes, in the judgment of the Investigator, in laboratory parameters (abnormalities) will be recorded as AEs.

During the treatment period, all Total WBC and WBC differential results will be blinded. If any of the following results are observed, the Investigator will be notified and asked to repeat the laboratory tests:

01 October 2014 Version 4.0

- Absolute lymphocyte count [ALC] < 200 cells/μL
- Absolute neutrophil count [ANC] < 1000 cells/μL
- Total WBC  $> 20,000 \text{ cells/}\mu\text{L}$

If the repeat values also exceed these limits, the Investigator will be informed that the patient's results for the abnormal parameter have fallen outside the acceptable thresholds.

If ANC or total WBC counts are confirmed outside the acceptable limits, the Medical Monitor will contact the treating investigator to request close monitoring for risk of infection and appropriate follow-up, at the discretion of the investigator.

If ALC results are confirmed as below 200 cells/ $\mu$ L, the investigator will be instructed that study drug is to be temporarily discontinued. Laboratory testing will be repeated weekly until the results have returned to within the following acceptable ranges:

• ALC  $> 500 \text{ cells/}\mu\text{L}$ 

When values have returned to acceptable values, the Investigator will be informed that the values are no longer outside of the acceptable range and that study drug may be restarted. (See Section 9.5.1 instructions on resuming treatment after dose interruptions.)

# 12.7. Abnormal Clinical Safety Findings

Clinically significant changes, in the judgment of the Investigator will be recorded as AEs.

# 12.8. Treatment of Overdose of Study Medication

An overdose is any dose of study treatment given to a patient or taken by a patient that exceeds the dose described in the protocol. There is no information regarding overdose with RPC1063. Any overdose, with or without associated AEs, must be promptly reported to Drug Safety Center. Overdoses do not need to be recorded as AEs in the eCRF; only in case of any AEs associated with the overdose, these should be reported on relevant AE/SAE sections in the eCRF.

# 12.9. Procedures in Case of Pregnancy

Pregnancy in itself is not regarded as an AE unless there is a suspicion that an investigational product may have interfered with the effectiveness of a contraceptive medication. However, the outcome of all pregnancies (spontaneous miscarriage, elective termination, normal birth or congenital abnormality) must be followed up and documented even if the patient was discontinued from the study.

Male patients should also be instructed to notify the treating investigator in the event that their female partner becomes pregnant. Attempts should be made to follow female partners of study patients, if they should become pregnant. The treating investigator must obtain informed consent from the pregnant partner of a study patient prior to collecting data on her pregnancy and its outcome.

All reports of congenital abnormalities/birth defects are SAEs. Spontaneous miscarriages should also be reported and handled as SAEs. Elective abortions without complications should not be handled as AEs. All outcomes of pregnancy must be reported to ...

#### 13. PLANNED STATISTICAL METHODS

#### 13.1. General Considerations

All patients will be randomized to either placebo (Part A) or IFN  $\beta$ -1a (Part B), RPC1063 0.5 mg, or RPC1063 1 mg in a 1:1:1 ratio, stratified by the following factors:

- EDSS at Baseline ( $\leq 3.5, >3.5$ )
- Country

All efficacy and safety data will be listed by patient. Baseline is defined as the last observed measurement prior to the Day 1 receipt of randomized study medication.

Descriptive statistics will consist of the number of patients (n), mean, standard deviation (SD), median, minimum, and maximum for continuous variables and counts and percentages for categorical variables.

A 11 1 .	1 1 1
All analyses using	or higher.
anaryses using	or menor.

# 13.2. Sample Size Estimation

### Part A

The primary analyses will compare the cumulative number of new GdE lesions at the end of Week 24 in each of the RPC1063 groups to the placebo group using a 2-sided Wilcoxon-Mann-Whitney test. For this type of nonparametric analysis, the parameter of interest for sample size/power considerations is the probability that a randomly selected patient in an active treatment arm will have fewer lesions than a randomly selected patient in the placebo arm. Limited data are available from which to estimate this parameter. However, based on the use of patient-level data from Tubridy et al. (1999) and Miller et al. (2003), estimates of this probability range from 0.634 to 0.754. Using the approach of Noether (1987), a sample size of 59 patients per group will provide 80% power to detect a difference if the true value of this probability is equal to 0.65 (Noether, 1987). Assuming a dropout rate of 15%, the planned enrollment is 210 patients (70 patients per arm).

#### Part B

Approximately 1200 patients with RMS will be randomized in this part of the study (approximately 400 per treatment group). The primary analyses will compare the ARRs in each of the RPC1063 groups to the IFN  $\beta$ -1a group using a Poisson regression model at the alpha = 0.025 level. The control ARR is assumed to be equal to 0.3 (Mikol, 2008). Assuming extra-Poisson variation ( $\sigma^2$ =1.3) (Polman, 2011) and 24 months of follow-up per patient, a total sample size of 999 patients (333 per arm) is estimated to provide 90% power to detect a 37% reduction in the ARR (i.e., an ARR of 0.19 for RPC1063) (Nicholas, 2011). In order to account for an assumed dropout rate of 17%, approximately 1200 patients (400 per arm) will be enrolled.

## 13.3. Statistical Analysis Plan

A Statistical Analysis Plan (SAP) will be written and finalized prior to any lock of the study database. The SAP will provide a detailed description of the statistical methods and expand on the details provided in the protocol. Additional analyses may be added. Tables, listing and figures shells will also be provided.

#### 13.4. Randomization

Patients will be randomized into the study on Day 1 using an IVRS provided by

#### Part A

 Patients will be randomized 1:1:1 to receive placebo, 0.5 mg RPC1063, or 1 mg RPC1063. The randomization will be stratified by country.

#### Part B

• Patients will be randomized 1:1:1 to receive IFN  $\beta$ -1a 30  $\mu$ g, 0.5 mg RPC1063, or 1 mg RPC1063. The randomization will be stratified by baseline EDSS ( $\leq$  3.5, > 3.5) and country.

Treatment groups are described in Section 9.5.1.

## 13.5. Analysis Populations

The following analysis populations will be used in the statistical analysis:

Intent-to-Treat (ITT): The ITT population will consist of all randomized patients who received at least 1 dose of study medication, with treatment assignment designated according to randomized treatment.

In Parts A and B, the primary efficacy analysis will be carried out in the intent-to-treat population.

Per Protocol (PP): The PP population will consist of the subset of the ITT population that excludes those patients who have had a major protocol violation. These will be defined prospectively, in advance of data lock and primary analyses, in the final SAP, by the (aggregate results blinded) project statistician. Membership in the PP population will be determined prior to unblinding.

Safety: The Safety population will consist of all patients receiving any study treatment and safety analyses will be carried out on this population according to highest dose of RPC1063 (up to 1 mg) actually received.

# 13.6. Statistical Methods

#### 13.6.1. Missing Data

#### Part A

Last observation carried forward (LOCF) and mean imputation will be used for patients with missing post-baseline lesions. If a patient is missing at most 2 post-baseline scans, then the last non-missing, post-baseline observation will be carried forward to impute the missing value.

However, if there are no values to be carried forward or if the patient is missing more than 2 scans, then the mean number of lesions from patients in the same treatment group at the same visit will be used as the imputed value. Sensitivity analyses will be specified in the SAP.

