#### Investigator decision

The Treating Investigator may discontinue study medication if it is determined that it is not safe or in the patient's best interest to receive further treatment. The Medical Monitor should be promptly notified of the decision.

- Noncompliance: after consultation between the investigator, the Medical Monitor, or Study Monitor, and the sponsor when appropriate, a patient may be discontinued from study medication for failure to comply with protocol requirements
- Intercurrent illness: A patient may be discontinued from study medication if, in the judgment of the treating investigator, the patient develops an intercurrent illness or complication that is not consistent with the protocol requirements or that, in any way, justifies discontinuation of study medication.
- Protocol-defined adverse events of special interest (see Section 12.4):
  - Confirmed AST or ALT >5 times the upper limit of the normal range, confirmed upon retest within 14 days of the original lab value (unless determined by the investigator to not be of hepatic origin)
  - o A diagnosis of macular edema, which is new or worsening since baseline
  - o FEV1 or FVC <50% of predicted values
- If the patient becomes pregnant
- Sponsor termination or suspension of the study

All patients who discontinue study medication should complete an Early Termination Visit (see Table 2 [Part A] and Table 4 [Part B]). Unless the patient withdraws consent or is lost to follow-up, they will be asked to undergo a follow-up visit 4 weeks after the last dose for the collection of safety data including lymphocyte recovery and to assess their disease status. Alternative treatment for multiple sclerosis (with the exception of medication given in the context of another clinical trial) can be started, if needed, after the early termination visit.

The reason for discontinuation of study medication will be recorded in the clinical records and the patient's eCRF.

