# 10.5. Early Termination Visit

Patients who prematurely discontinue study treatment will be asked to complete an early termination visit. The following assessments will be performed:

- Blood/urine sampling for the following laboratory tests:
  - Hematology: RBC count, total and differential WBC count (basophils, eosinophils, lymphocytes, monocytes, and neutrophils), platelet count, hemoglobin, hematocrit, MCV, MCH, and MCHC
     Note: All total WBC and differential WBC counts will be blinded during the study.
  - Blood chemistry: sodium, potassium, chloride, calcium, magnesium, phosphate, blood urea nitrogen, random glucose, albumin, alkaline phosphatase, creatinine, SGPT/ALT, SGOT/AST, GGT, amylase, total bilirubin, conjugated bilirubin, hemoglobin A1c. Abnormal laboratory parameters inconsistent with clinical presentation of MS or suspicious of underlying medical condition should be repeated for accuracy. If an increase of amylase above the clinically notable value (≥ 300 U/L) is observed at any post randomization visit, lipase should be tested to determine the origin of elevated amylase (pancreatic versus extra pancreatic)
  - Urinalysis: leukocytes, specific gravity, bilirubin, blood, glucose, ketones, pH, protein, and urobilinogen
  - Urine beta-hCG (females of childbearing potential only). If the urine pregnancy test is positive, do not dose and confirm with a serum pregnancy test.
  - Coagulation panel: PT and partial thromboplastin time PTT
  - sTSH

- PK sampling
- Complete physical examination: including evaluation of heart, lung, head and neck, abdominal, neurological, skin, and extremities
- Weight
- Vital signs: body temperature, blood pressure and heart rate
- 12-lead ECG
- Review study drug accountability and compliance
- Brain MRI
- EDSS and neurological examination
- MSFC and LCLA
- MSQOL-54
- Pulmonary function tests including FEV1, FVC, and DLCO measurements
- OCT evaluation
- Dermatological examination
- Suicidality assessment using the C-SSRS
- Record concomitant therapy
- Record AEs/SAEs

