## **13.6.4.** Efficacy

#### Part A

For the primary analysis, the cumulative number of GdE lesions from Week 12 to Week 24 will be compared between the 1 mg RPC1063 group and the placebo group using the stratified Wilcoxon-Mann-Whitney test, stratified by presence of GdE lesions at baseline (absent or present). This comparison will be assessed using a 2-sided test at the alpha=0.04944 level of significance (to keep the overall Part A level of significant at alpha=0.05, accounting for the O'Brien-Fleming adjustment and interim analysis) (Reboussin, 2000). If the comparison between the 1 mg RPC1063 group and placebo is statistically significant, then a second primary analysis will similarly compare the 0.5 mg RPC1063 group and the placebo group, also based on a 2-sided test at the alpha=0.04944 level of significance. Sensitivity and descriptive analyses will also be presented.

The secondary endpoint of the proportion of patients free of GdE lesions at Week 24 will be analyzed using a logistic regression model with treatment group (three levels) and presence of baseline GdE lesions (absent, present) as factors. Pairwise comparisons between the 1 mg RPC1063 group and placebo, and between the 0.5 mg RPC1063 group and placebo, will be tested.

Quantitative endpoints such as the percent brain volume change over 24 weeks will be analyzed using analysis of covariance models with treatment group as a factor and the baseline value of the corresponding parameter as a covariate.

Endpoints that are defined in terms of lesion counts will be analyzed using the Wilcoxon-Mann-Whitney test. These analyses will include only the two groups being compared.

All secondary endpoints will be analyzed using 2-sided tests at the 5% level of significance.

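### Part A gives patients missing more than two scans their own arm's mean lesion count before the primary rank test; at 15% evenly timed dropout the simulated type I error is about 0.06 to 0.08, against the stated 0.04944

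*Protocol*

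**What the plan says.** Protocol section 13.6.1 (Missing Data, Part A) has two tiers. The first is last observation carried forward: "If a patient is missing at most 2 post-baseline scans, then the last non-missing, post-baseline observation will be carried forward". The second covers patients missing more than two scans, or with no post-baseline value to carry: "then the mean number of lesions from patients in the same treatment group at the same visit will be used as the imputed value". Only sensitivity analyses are left to the SAP.

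Section 13.5 fixes the population: "In Parts A and B, the primary efficacy analysis will be carried out in the intent-to-treat population". Section 13.6.4 then has the Week 12-24 lesion total "compared between the 1 mg RPC1063 group and the placebo group using the stratified Wilcoxon-Mann-Whitney test", stratified by presence of GdE lesions at baseline, at two-sided 0.04944. The stated purpose of that level is "to keep the overall Part A level of significant at alpha=0.05", given the interim analysis. Section 13.2 assumes 15% dropout and plans 70 patients per arm.

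On scans after treatment stops, section 10.5 says: "Patients who prematurely discontinue study treatment will be asked to complete an early termination visit". Its list of assessments includes a brain MRI; the follow-up list in section 10.6 does not. The protocol does not say which scheduled scan the early-termination MRI stands for. Section 2 of the supplied SAP says that Part A has its own SAP, which was not among the documents.

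**The concern.** A rank test's null variance assumes that patients are exchangeable between arms. Own-arm mean imputation breaks this. If one arm's observed mean is higher by chance, every mean-imputed patient in that arm is moved up together. Patients with no Week 12-24 scan receive identical totals within their arm. The test counts these copies as separate patients, although they carry no new information and always point the same way as the chance difference.

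At stake is the error rate of the Part A efficacy claim. The sponsor lowered the final level by 0.05 - 0.04944 = 0.00056 to pay for the interim look. An unallowed-for excess of one or more percentage points outweighs that correction many times over.

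**Working it through.** **The plan's own figures reproduce.**
- Noether: N = (1.960 + 0.842)² / [12 × 0.25 × (0.65 - 0.5)²] = 116.3 in total, or 58.1 and so 59 per arm. 59 / 0.85 = 69.4, so 70 per arm.
- Lan-DeMets spending with O'Brien-Fleming boundaries at information fraction 0.45 (section 13.6.7) gives 0.00167 and 0.04944.

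**Who is mean-imputed.** Post-baseline scans are at Weeks 8, 12, 16, 20 and 24 (section 9.1). A first missing scan at Week 8, 12 or 16 leaves 5, 4 or 3 scans missing, so the mean applies. A first missing scan at Week 20 or 24 leaves 2 or 1, so LOCF applies. With 15% dropout spread equally over the five scans, 3/5 × 15% = 9% of patients are mean-imputed (0.09 × 70 = 6.3 per arm). If the early-termination scan fills the next slot, this becomes 2/5 × 15% = 6%.

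**Null simulation of the written rule.**
- 70 per arm, monotone dropout unrelated to outcome, van Elteren test at two-sided 0.04944.
- Assumed, because the documents do not give it: gamma-Poisson lesion counts with mean 0.8 or 1.5 per scan and frailty variance 3 or 5. Ranges below are over these four models.
- 8,000 runs per model and setting; Monte Carlo standard error √(0.05 × 0.95 / 8,000) = 0.0024.

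| Dropout, placebo / active | First missing scan | Early-termination scan not used | Fills next slot |
|---|---|---|---|
| 15% / 15% | even over five scans | 0.073-0.079 | 0.059-0.062 |
| 15% / 15% | Week 8, 12 or 16 | 0.098-0.110 | 0.075-0.080 |
| 15% / 15% | Week 8 or 12 | 0.107-0.116 | 0.096-0.106 |
| 15% / 15% | Week 20 or 24 | 0.048-0.051 | 0.049-0.052 |
| 5% / 5% | even | 0.051-0.057 | 0.053-0.055 |
| 5% / 5% | Week 8 or 12 | 0.058-0.064 | 0.057-0.058 |
| 10% / 20% | even | 0.079-0.086 | 0.063-0.067 |
| 10% / 20% | Week 8, 12 or 16 | 0.127-0.138 | 0.084-0.095 |

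The late-dropout row uses only the LOCF tier and shows no inflation, so the cause is the mean tier.

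A second simulation used five lesion models (mean 0.8-2 per scan, gamma shape 0.15-1.0) and 20,000 trials each:
- 15% dropout, even by scan: 0.072-0.077 without the early-termination scan and 0.060-0.065 with it.
- 15% dropout, even in calendar time: 0.073-0.084 and 0.066-0.073.
- No dropout: 0.048.

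**Size of the excess.** At 15% and even timing by scan it is 0.059 - 0.04944 = 0.0096 to 0.079 - 0.04944 = 0.0296, roughly 17 to 53 times the 0.00056 interim correction.

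**Alternatives.**
- Ranking only patients with at least one Week 12-24 scan, on the mean of their available scans, gave 0.042-0.056 over 38 settings. These covered 15/15, 5/5, 10/20 and 5/25% at four timings and 10/10% at three, each with and without the early-termination scan.
- A mean pooled over both arms is not a safe substitute. It held 0.047-0.051 with equal, evenly timed dropout. With all dropout before Week 12 and no early-termination scan, it gave 0.064-0.085 at 10% vs 20% and 0.121-0.178 at 5% vs 25%.

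**The case against.** - **The Part A SAP is unseen.** Section 13.3 makes the SAP the place for detailed methods, and assigning the early-termination scan to a visit is ordinary SAP content. This stands as a limit: the point concerns the protocol text. That text makes own-arm means the primary rule and defers only sensitivity analyses.
- **The size rests on assumptions.** Timing and lesion distribution are not documented, and results run from no inflation to 0.116 at 15% in both arms. This stands, and is why ranges are given.
- **15% is a planning allowance, and the scan would probably be used.** Section 9.4.4.1 says: "All patients who discontinue study medication should complete an Early Termination Visit". That favours the lower figures, which still exceed the level unless dropout is late or near 5%.
- **Little depends on it.** Part B starts on the DMC's review of interim data, not on this test. This stands.
- **The remedy is not neutral.** It drops some dosed, randomized patients from the ranking, and its level control assumes uninformative dropout. With placebo dropout concentrated in high-lesion patients, before Week 16 and without the early-termination scan, it gave 0.070-0.078 (placebo 20%, active 10%) and about 0.10 (25%, 5%). The written rule gave 0.25-0.32 there, so this is no defence of it. A re-randomization test that repeats the imputation in each permutation would keep every patient; it was not evaluated.
- **Timing of the change.** Section 9.1 unblinds the sponsor and CRO once Week 24 data are final, and the documents do not say whether that has happened. If it has, the change is no longer prespecified.

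**Conclusion.** The concern holds. Followed as written, the protocol's primary Part A test exceeds its stated level whenever an appreciable share of patients drop out early enough to be mean-imputed. At the planned 15%, evenly timed by scan, type I error is about 0.06 with the early-termination scan and 0.07-0.08 without it. It is about 0.10-0.12 if all dropout precedes Week 12, nominal if all is late, and less than one point above nominal at 5% evenly timed.

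The figures are for 1 mg against placebo at the final analysis, without the small interim spend. They assume gamma-Poisson lesions and uninformative dropout. The direction is secure; confidence in the size is medium. The rule should be changed, but the consequence is confined to the Part A claim.

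**What to change.** In Protocol section 13.6.1 and the Part A SAP:
- Remove own-arm mean imputation from the primary analysis.
- Rank each patient's mean GdE count per available Week 12-24 scan, for all ITT patients with at least one such scan, with no imputed values. Multiplying by 4 puts it on the scale of the four-scan total and does not affect the ranks.
- Assign an early-termination scan to the nearest scheduled scan visit, keeping the scheduled scan where that visit already has one.
- Use an arm-blind value for patients with no Week 12-24 scan in a sensitivity analysis only, and keep the present LOCF and own-arm mean rule as a second one.

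In section 13.5, name the subset with at least one Week 12-24 scan as the Part A primary analysis set.

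**Cost.** Wording, plus some patients leaving the ranking. At 15% dropout these are 6% (even timing), 10% (before Week 16) or 15% (before Week 12) without early-termination scans, and 3%, 5% or 7.5% with them. At the planning effect of 0.65 (rate ratio 0.10-0.24 in these models), simulated power is at least 0.986, against at least 0.992 as written. Both are high because of ties and the prognostic baseline stratum in the models. At an assumed weaker rate ratio of 0.4, nominal power falls by 2-3, 6-7 or 7-8 points for the three timings without early-termination scans, and by about 1, 1-3 or 5-7 points with them. That loss is removed inflation: at equal true size the new rule has 1-8 points more power.
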